2.2.2 Secondary Study Objectives

The secondary objectives to be evaluated among ADA-SCID subjects treated with a cryopreserved formulation of OTL-101 include confirmation of the overall survival and event free survival at 24 months, safety evaluation including infection rates, quality of life and immune response.

2.2.3 Exploratory Study Objectives

Exploratory objectives include the measurement of biological correlates of efficacy including; percentage of gene marking in peripheral blood granulocytes, vector integration analysis, quantification of clonal diversity of vector integrants, T-cell receptor excision circle (TREC) and fluorescence-activated cell sorting (FACS) for T-cell receptor (TCR) V- β family use, ADA enzyme activity in erythrocytes, total adenine nucleotides in erythrocytes, and immune reconstitution.

3 STUDY DESIGN

3.1 General Design and Study Scheme

This is a prospective, non-randomized, single-cohort, longitudinal, single-center, clinical study designed to assess the efficacy and safety of OTL-101 cryopreserved formulation administered in ADA-SCID subjects aged between ≥ 30 days to < 18 years of age, who are not eligible for an HLA-matched sibling/family donor and meeting the inclusion/exclusion criteria. This study aims to recruit 10 evaluable subjects.

The aim of this clinical study is also to assess the success of treatment at the subject level (“responder analysis”) 6 months post OTL-101 infusion, using predictive criteria for overall survival and event free survival and to compare this with data obtained from one of the ongoing Phase I/II clinical studies using the fresh formulation of OTL-101.

Once informed consent has been obtained, the subjects enrolled will be screened to determine their full eligibility for participation over 1 month.

Eligible subjects will be hospitalized to undergo the harvesting of autologous CD34+ cells. A backup harvest of non-transduced CD34+ cells will be obtained during the harvesting procedure to be used in the event of i) product damage during the thawing of OTL-101 that would prevent infusion of the product although the patient has already been conditioned or ii) lack of engraftment/hematopoietic reconstitution 42 days post infusion of OTL-101. A failure of hematologic reconstitution is defined as persistent ANC $< 200/\mu\text{l}$ or platelets $< 20,000/\mu\text{l}$ on three independent and consecutive determinations over at least ten days after day 42 from the day of OTL-101 infusion.

OTL-101 is a cryopreserved formulation of autologous CD34+ hematopoietic stem cells transduced *ex vivo* with EFS LV encoding for the human *ADA gene* (OTL-101). To enable the release of the OTL-101 product for infusion, the cryopreserved OTL-101 product must meet various quality control criteria for safety, identity, viability, purity and potency. If OTL-101 meets the acceptance criteria and is released, the subjects will be readmitted for conditioning with Busulfan. The OTL-101 product will be infused after a minimal interval of at least 24 hours following the completion of Busulfan administration. Subjects may remain as an in-patient following autologous transplantation for approximately three to 35 days.

For subjects who have successfully received the OTL-101 product, PEG-ADA ERT use will be evaluated at the 1 Month follow-up visit (30 days post treatment ± 7 days) and discontinued at Day 30 (-3/+15) after the transplant. Hematologic reconstitution will be assessed at Day 42 (± 7 days), and in the event of no reconstitution the backup HSC sample will be administered, if the investigator believes this is in the subject's best interest. The subjects will then be seen at regular intervals to review their history, perform examinations and draw blood samples at Months 3, 6 and 9 (all ± 2 weeks) as well as Months 12, 18 and 24 (all ± 4 weeks). Any medically-indicated interventions, including the need to reinstate PEG-ADA ERT, will be assessed at all follow-up visits after Month 1. Hematopoietic reconstitution will be assessed again at the Month 6 visit and if there is still no evidence of cellular recovery, the subject will be given ERT and/or HSCT, if available and deemed appropriate by the Investigator. After the Month 24 visit, the subjects will have completed the study and may enter a long term registry.

This study will include three statistical analyses:

1. The first analysis will compare the success/failure data 6-months post OTL-101 infusion between fresh and cryopreserved OTL-101 formulations. The success/failure of OTL-101 will be defined by the three criteria listed in the primary objectives ([Section 2.2.1](#)). This data will be compared with available data from one of the ongoing Phase I/II studies using the OTL-101 fresh formulation. This will support the CMC comparability data between OTL-101 cryopreserved and fresh formulations. Secondary and exploratory endpoints will also be described.
2. The second analysis will determine the 12 month overall survival and event free survival for all subjects. Secondary and exploratory endpoints, as well as baseline characteristics, subject disposition, and safety data will also be described.
3. The third and final analysis will be performed to determine the overall survival and event free survival for all subjects 24 months post OTL-101 infusion. Secondary and exploratory endpoints, as well as baseline characteristics, subject disposition, safety and Busulfan pharmacokinetic (PK) data will also be described.

Efficacy analyses will be primarily descriptive in nature.

The study will be overseen by an independent Data Safety Monitoring Board (DSMB), who will review the nature and severity of emerging safety data during the study. The DSMB will also liaise with the Principal Investigator directly to ensure the safety of participants during the study. The Investigator, subjects and their families will be informed about any significant emerging safety data.

The study schema is provided in [Figure 1](#) below.

[figure not shown]

Figure 1: Study Scheme

Backup sample will be taken in the event of product damage or failure to achieve hematopoietic reconstitution.

* The timeframe for the cryopreservation process may vary.

Abbreviations: ADA= Adenosine deaminase, AUC = area under the curve, BM = bone marrow, EFS = Elongation Factor 1 α Short form, ERT = enzyme replacement therapy, LV = lentivirus vector.

3.2 Primary and Secondary Evaluations and Endpoints

3.2.1 Primary Efficacy Evaluations and Endpoints

The primary efficacy endpoints for this study include:

1. Evaluation of OTL-101 at 6 months, post OTL-101 infusion, in support of CMC assessing comparability of cryopreserved and fresh formulations, by evaluating the success of therapy for each subject based on all three parameters listed below and their thresholds being met:
 - a) Erythrocyte ADA enzyme activity above baseline/pre-treatment level (>0 Units),
 - b) Absolute CD3+ T-cell counts $\geq 200/\text{mm}^3$, and
 - c) Peripheral blood samples positive for vector sequences by qPCR($\geq 1/10,000$ cells).

Please note: Subjects not meeting any one criterion will be designated a failure (non-responder). Further details are described in [Section 3.6.1](#).

This data will be compared with subject data from the Phase I/II study using the fresh formulation.

2. Evaluate the overall survival and event free survival 12 months post OTL-101 infusion. Overall survival is defined as the proportion of subjects alive. Event-free survival is defined as the proportion of subjects alive with no “event”, an “event” being the resumption of PEG-ADA ERT or the need for a rescue allogenic HSCT, or death.

Full descriptions of the efficacy assessments are presented in [Section 7.1](#).

3.2.2 Secondary Efficacy Evaluations and Endpoints

Secondary efficacy endpoints include:

- Evaluation of the overall survival and event free survival 24 months post OTL-101 infusion.
- Use of immunoglobulin replacement therapies prior to and after OTL-101 infusion.
- Performance outcomes and quality of life measured by the Karnofsky/Lansky scale and questions relevant to general well-being, school attendance and ability to practice sports, respectively.
- Rates of severe infections/opportunistic infectious episodes, defined as infections or severe infections requiring hospitalization or prolonging hospitalization and/or documented infections by opportunistic pathogens (e.g. interstitial pneumonia, intractable diarrhoea).
- Response to tetanus vaccination.
- Immune reconstitution: T and B cell reconstitution.

Full descriptions of the efficacy assessments are presented in [Section 7.1.2](#).

3.2.3 Safety Evaluations and Endpoints

The safety and tolerability of OTL-101 will be assessed throughout the study by evaluating adverse events (AEs), clinical laboratory test results, vital signs measurements, electrocardiogram (ECG), physical examination results, and concomitant medication usage. In

addition, the safety of OTL-101 will be assessed through monitoring infections and any emergence of replication competent lentivirus, monoclonal expansion or leukemia due to chosen vector.

Full descriptions of the safety assessments are presented in [Section 8](#).

3.2.4 Exploratory Endpoints and Evaluations

The exploratory endpoints will include laboratory correlates of efficacy that will be used to assess the level of gene correction, engraftment and immune reconstitution:

- Quantification of clonal diversity of vector integrants.
- TREC and FACS for TCR V-beta family use.
- Percentage gene marking in peripheral blood cells.
- Adenosine deaminase enzyme activity in erythrocytes.
- Total adenine nucleotides in erythrocytes.
- Vector integration analysis.
- Immune reconstitution
 - Absolute Lymphocyte Count.
 - Absolute numbers of T, B, NK lymphocytes in peripheral blood.
 - T lymphocyte proliferative responses to mitogen (PHA) and to antigens (tetanus toxoid after vaccination)
 - Serum immunoglobulin levels (IgG, IgA and IgM).

3.3 Randomization and Blinding

This is a non-randomised study and there is no blinding.

3.4 Protocol Treatment and Dosage

OTL-101 comprises autologous, CD34⁺ HSCs transduced *ex vivo* with EFS-ADA LV, formulated and cryopreserved in CryoStor[®] CS5. The OTL-101 product will be manufactured using HSCs purified from the subject's BM. To enable its release for administration, the OTL-101 product must meet the acceptance criteria for a series of Quality Control assays of safety, identity, viability, purity and potency.

The dose of genetically-modified cells comprises a single administration of 2.0 to 20 x 10e6 CD34⁺ cells/kg.

A detailed description of the procedures for the administration of the OTL-101 product is provided in [Section 3.7](#).

3.4.1 Protocol Treatment

OTL-101 is manufactured under Good Manufacturing Practice (GMP) guidelines, using the subject's own CD34⁺ HSCs. OTL-101 is formulated in Cryostor CS5, filled into cryobags, cryopreserved and then stored in the vapor phase of liquid nitrogen (LN₂). Final product dose and infusion volume calculations are described in [Section 6.1.1](#) and [Section 17: Appendix 1](#). On the day the subject is to be infused, the cryopreserved OTL-101 product bag(s) will be transported to the bedside in a dry nitrogen shipping container. Immediately prior to infusion,

the bag(s) will be removed from the shipping container and thawed using either a plasma thawing device or a pre-warmed water bath (using sterile water). For thawing, the OTL-101 product bag(s) will be placed in an outer bag sleeve in case of a leak. After thawing, the OTL-101 product bag(s) will be attached to a sterile intravenous line fitted with a three-way stopcock and sterile syringe. The cells will be pulled into the syringe from the bag(s), the stopcock will be turned and then the contents of the syringe will be pushed through the intravenous line into the recipient. The OTL-101 product will be labeled as the Study Agent. Please note: when more than one bag is required to be infused, only one OTL-101 product bag per hour will be administered ([Section 6.1.1](#)).

3.5 Duration of Subject Participation

The study will consist of the following periods:

- Screening: approximately 2 months
- Bone marrow harvest of autologous cells: 1 day
- Manufacture and release of OTL-101: 30-45 days
- Pre-conditioning prior to transplant: 4 days
- OTL-101 administration: this may entail up to 4-6 weeks of in-patient stay, either at UCLA or the subject may be transferred from UCLA to a home hospital at 3-7 days post-transplant for the pursuit of subsequent hospitalization for up to 4-6 weeks.
- Post treatment follow-up: 2 years after the administration of OTL-101.

The total study duration for each subject is estimated to be up to 2 years and 4 months.

The study will start when the first subject has signed the informed consent form. Each subject's participation in the study will end at the time of his/her last visit, or death. The study will have ended after the last subject has completed the last study visit at 24 months post OTL-101 infusion, however the primary endpoints for this study will be overall survival and event free survival at 12 months post OTL-101 infusion.

On completion of their participation in this study, subjects will be invited and encouraged to participate in a registry for long term data collection according to guideline recommendations.

3.6 Stopping Rules and Discontinuation Criteria

3.6.1 Subject Stopping Rules and Criteria for Discontinuation

If any one of the following instances occur, all new enrollments to the protocol or the treatment of subjects will be halted, pending investigation of the cause and discussion with the DSMB for final recommendation/decision:

1. If there is one death or two Grade 4 treatment-related toxicities (see [Section 8.2.1.1](#) for severity definitions). Please note Grade 4 Busulfan-related hematologic AEs such as transient leukopenia, anemia, thrombocytopenia that are anticipated, and have resolved within 42 days of transplant will not be considered a stopping rule.
2. If two subjects experience prolonged unresponsive pancytopenia, defined as an initial failure of hematologic reconstitution which does not improve following the administration of the subject's autologous back-up cells. A failure of hematologic reconstitution is defined as persistent ANC < 200/ μ l or platelets < 20,000/ μ l on three

independent and consecutive determinations over at least ten days after day 42 from the day of OTL-101 infusion.

If, at Day 90 following the initial infusion of OTL-101, the failure of hematologic reconstitution persists after the subject's autologous back-up cells have been infused, the subject can be said to be experiencing prolonged unresponsive pancytopenia. The subject should then receive standard care for pancytopenia.

3. If RCL is detected, and confirmed in one subject.
4. If a subject in the study develops hematological proliferative, monoclonal expansion or malignant disease (excluding dermatofibrosarcoma protuberans (DFSP)). A thorough investigation of the cause of the proliferation, expansion or malignancy, including proviral integration analysis, will be carried out.
5. If there are three non-responders, as defined in the primary endpoint criteria ([Section 3.2.1](#)), who will be designated an OTL-101 treatment failure and will be withdrawn from the study to permit further treatment with PEG-ADA ERT, or HSCT if available.

Any such finding will be discussed with the Sponsor and DSMB, and an agreement should be made and documented to detail the conditions under which the study can be resumed before enrolling the next subject. Evaluations of the study endpoints of subjects already enrolled and who have received OTL-101, will continue.

A subject may discontinue participation in the study at any time for any reason (for example lack of efficacy, withdrawal of consent, AE). The Investigator and/or Sponsor can withdraw a subject from the study at any time for any reason (for example protocol violation or deviation as defined in [Section 4.3](#), non-compliance with the protocol, or AE).

The Investigator should assess the ongoing risk-benefit ratio of each subject during their participation in the study, in consideration of any AEs and the potential benefits of continued treatment with OTL-101 or any alternative therapies.

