and re-infused to overcome more severe myelosuppressive effects of the conditioning regimen. If the failure of hematologic reconstitution persist after the back-up marrow has been given through day 90 from the initial infusion of the cell product, prolonged unresponsive pancytopenia will exist.

If the Investigator considers the use of the back up HSC sample is not in the best interests of the subject, rescue medication, as per standard institute protocols, will be implemented. Any treatment administered to the subject will be recorded in the eCRF. Adverse events will also be recorded.

Month 3 (Visit 6 - +/- 2 weeks)

- Physical examination, vital signs, height, weight and interval history (including routine review of systems, including infectious symptoms (e.g., fever), AEs and concomitant medications),
- Assessment of re-initiation of PEG-ADA therapy and use of IgG replacement therapy will be documented. Please note: subjects should have discontinued PEG-ADA treatment at Visit 4 (Month 1/Day 30),
- Hematology and biochemistry panels,
- RCL assay in PBMC,
- Serum to be banked for possible Western blot testing for RCL (testing performed if the RCL assay in PBMC returns a positive result),
- Monitoring for severe infections and/or opportunistic infectious episodes at each study visit,
- Vector integration analysis,
- Immune function testing:
 - o Determination of absolute numbers of CD3+, CD4+ and CD8+ T-lymphocytes, CD19+ B-lymphocytes and CD56/CD16+ (or CD56+/CD3-) NK cells, CD4+/CD45RA+ (naïve) and CD4+/CD45RO+ (memory) T cells:
 - o Serum immunoglobulin (IgG, IgA, IgM),
- Gene transduction/expression:
 - o Measurement of the proportion of cells containing the inserted *ADA gene* in PBMC and granulocytes and/or lineage-sorted cells,
 - o Measurement of ADA expression in erythrocytes by ADA enzymatic assay and deoxyadenine nucleotides in RBC.

Month 6 (Visit 7 - +/- 2 weeks)

- Physical examination, vital signs, height, weight and interval history (including routine review of systems, including infectious symptoms (e.g., fever), AEs and concomitant medications),
- Evaluation of quality of life using the Karnofsky/Lansky scale and questions relevant to general well-being, school attendance, and ability to practice sports, respectively,
- Assessment of re-initiation of PEG-ADA therapy and use of IgG replacement therapy will be documented. Please note: subjects should have discontinued PEG-ADA treatment at Visit 4 (Month 1/Day 30),

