6.1.2 Rescue Administration of Autologous HSC Backup

If a subject has not achieved hematopoietic reconstitution at Day 30 (Month 1 visit), he/she will be closely monitored as per standard medical management in order to determine the need for a rescue administration of the autologous back-up. A rescue administration will be given according to the physician's criteria if reconstitution is not observed by Day 42. Subjects may receive transfusions to give more time to observe whether signs of hematopoietic reconstitution are seen. This is not documented in the Schedule of Events tables as rescue procedures would follow standard institute protocols.

- A failure of hematologic reconstitution is defined as persistent ANC < 200/ μ l or platelets < 20,000/ μ l on three independent and consecutive determinations over at least ten days after day 42 from the day of OTL-101 infusion.

If these conditions are fulfilled, the subject's autologous back-up cells will be infused according to standard institute protocols.

If, at Day 90 from the initial infusion of OTL-101, a failure of hematologic reconstitution persists after the subject's autologous back-up cells have been infused and the subject is experiencing prolonged unresponsive pancytopenia, the subject will be withdrawn from the study.

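### Halting rule 2 counts persistent engraftment failure only if back-up cells were infused, so a child still in failure at Day 90 without back-up is left to rule 1 and its causality judgement

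*Protocol*

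**What the plan says.** **Rule 2 (Protocol 3.6.1).** Two subjects with prolonged unresponsive pancytopenia trigger a halt pending investigation and DSMB discussion. The condition is "defined as an initial failure of hematologic reconstitution which does not improve following the administration of the" subject's autologous back-up cells. The Day 90 sentence repeats the requirement: only once the "back-up cells have been infused, the subject can be said to be experiencing prolonged unresponsive pancytopenia". Protocol 5.1.7 (Day 42 visit) matches this, placing the persisting failure "after the back-up marrow has been given through day 90 from the initial infusion of the cell product". Failure itself is a blood-count definition: ANC below 200/µl or platelets below 20,000/µl on three consecutive determinations over at least ten days after Day 42.

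**Whether back-up is given.** The text is mixed:
- Protocol 3.1: "the backup HSC sample will be administered, if the investigator believes this is in the" subject's best interest.
- Protocol 5.1.7, after giving the formal failure definition: "If the Investigator considers the use of the back up HSC sample is not in the best interests of the subject, rescue medication" is used instead.
- Protocol 6.3 says only that back-up may be given. Footnote 1 to Table 2 mentions only rescue medication at Day 42.
- Protocol 6.1.2 refers to the physician's criteria and allows transfusions to gain time, but says that once the failure definition is met the "back-up cells will be infused according to standard institute protocols".
- SAP 8.2.12 plans to tabulate reasons for a lack of back-up cells.

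**Rule 1 (Protocol 3.6.1).** "If there is one death or two Grade 4 treatment-related toxicities". Anticipated Grade 4 hematologic events related to Busulfan that "have resolved within 42 days of transplant will not be considered a stopping rule".

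**The concern.** Rule 2 is the halt that rests on blood counts. As worded, whether a child counts also depends on which rescue was chosen. Two children with the same counts at Day 90 are treated differently if one received back-up and the other received rescue medication or had no usable back-up. The second child can reach a written halting rule for cytopenia only through rule 1, which adds an attribution step.

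This matters because Protocol 1.4.2.1 lists poorer recovery, including the need to return unmodified marrow, as a risk specific to the cryopreserved product. Protocol 2.1 reports only three earlier subjects given cryopreserved cells, with a different cryoprotectant.

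**Working it through.** The plan states no operating characteristics for its halting rules, so there is no figure to reproduce. The check is mainly textual.

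**Step 1. Who counts under rule 2 at Day 90**

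| State at Day 90 | Rule 2 as written | Rule 2 with the fix |
|---|---|---|
| Failure persists, back-up infused | counts | counts |
| Failure persists, back-up withheld or lacking | does not count | counts |
| Recovered, with or without back-up | does not count | does not count |

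Only the second row changes. With two children in failure at Day 90 and back-up withheld from one, rule 2 counts 1 of the 2 needed.

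**Step 2. Does rule 1 cover the second row?**
- *Severity.* Rule 1 grades by Protocol 8.2.1.1, which points to the appended toxicity table. Grade 4 there is ANC below 400/mm³ (over 7 days of age) or platelets below 25,000/mm³. The failure thresholds of 200 and 20,000 lie inside Grade 4.
- *Timing.* The Busulfan exemption covers only events resolved within 42 days. Rule 1 does not wait for formal failure, which cannot be met before 42 + 10 = Day 52. It can fire from about Day 43, some 90 − 43 = 47 days before rule 2's Day 90 reading.
- *Recording.* Under Protocol 8.2.1.4 a laboratory abnormality is an adverse event if it needs intervention or diagnostic evaluation, or is judged clinically significant. Rescue treatment would normally satisfy this.
- *Attribution.* Protocol 8.2.1.2 classifies relation to OTL-101 administration. Not related requires good reasons to rule out causality, which favours counting. But attribution to other drugs is one of its examples, and 5.1.7 describes back-up as overcoming the myelosuppressive effects of conditioning. The Busulfan note in rule 1 implies that unresolved conditioning-related cytopenia can count, but does not say so.

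Rule 1 would therefore usually fire, subject to two judgements that rule 2 does not require.

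**Step 3. Other rules.** Rule 5 needs three Month 6 non-responders on ADA activity, CD3 count and vector marking. ANC and platelets are not among its criteria.

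**Step 4. Illustration only.** Suppose exactly two persistent failures and no other rule 1 event. Let *w* be the chance that a child has no back-up, and *c* the chance that the child's event is recorded and judged related, all independent. Neither rate is in the documents.
- Rule 2 not met: 1 − (1 − w)². For w = 0.10, 0.25, 0.50 this is 0.19, 0.44, 0.75.
- Neither rule met, one toxicity per child: [1 − (1 − w)²](1 − c²).
- Neither rule met, two cytopenias per child counted separately with one attribution per child: [1 − (1 − w)²](1 − c)².

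| w = 0.25 | c = 0.50 | c = 0.75 | c = 0.90 | c = 1.00 |
|---|---|---|---|---|
| One toxicity per child | 33% | 19% | 8% | 0% |
| Two toxicities per child | 11% | 3% | 0.4% | 0% |

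With one toxicity per child, the first row becomes 14%, 8%, 4%, 0% at w = 0.10 and 56%, 33%, 14%, 0% at w = 0.50.

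These condition on two failures having occurred. For 10 treated subjects with an assumed failure risk of 5% or 10%, exactly two failures has probability 0.075 or 0.194. At w = 0.25 and c = 0.90, with one toxicity per child, exactly two failures with neither rule met has probability 0.075 × 0.083 = 0.6% or 0.194 × 0.083 = 1.6%.

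**The case against.** **Unresponsive means that back-up was tried.** A child never given back-up has not been shown to be unresponsive to it, so counting that child changes the construct. This is fair for a diagnostic label. It is weaker for a halting count, which only pauses enrolment or treatment for review while follow-up of treated subjects continues. A child still below the failure thresholds at Day 90 merits that review whichever rescue was used.

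**Protocol 6.1.2 says back-up will be infused once formal failure is met.** This makes back-up the default and the affected case uncommon. It does not close the gap: 5.1.7 allows withholding after stating the same failure definition, and cells that do not exist cannot be infused.

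**Rule 1 already covers it.** Largely true, as Step 2 shows, and it can act well before Day 90. What stands is its dependence on recording and attribution.

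**The fix could redirect care.** In 3.6.1 the Day 90 sentence leads to standard care for pancytopenia. Redefining the label outright could steer a child with unused back-up away from it. This objection is right, and it shapes the fix below.

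A reader might infer that two children could remain in failure without anyone acting. The documents do not support that: the DSMB reviews emerging safety data (3.1), serious events are reviewed as reported, and the sponsor may terminate at any time (3.6.2). The gap lies in the written trigger, not in whether the event is seen.

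**Conclusion.** The point holds in a limited form. As written, a child in failure at Day 90 without back-up cannot count toward rule 2, and no text elsewhere lets that child count. This follows from the wording and needs no assumed rates.

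The consequence is small. Back-up is the default, and rule 1 would usually capture two such children. What remains is that, for them, a blood-count halt is replaced by one that needs an adverse event record and a treatment-related judgement.

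A reader might take the 44% or 33% in the illustration as the chance that the safeguard fails. The documents do not support that. Both figures assume that two failures have already occurred and use invented withholding or attribution rates; the 44% also ignores rule 1. If every event is recorded and judged related, the chance that neither rule is met is zero. This is a minor safety-rule improvement, not a defect that leaves subjects unprotected.

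**What to change.** In rule 2 (Protocol 3.6.1) and the matching text in 5.1.7, say that, for the purpose of the halting count, a subject counts if failure of hematologic reconstitution persists at Day 90 after OTL-101, whether or not autologous back-up cells were infused.

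Add that being counted does not preclude later infusion of unused back-up cells. Keep the standard-care sentence in 3.6.1 and the withdrawal text in 6.1.2 conditional on back-up having been given, so that a child with unused back-up is neither redirected nor withdrawn by the change.

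The cost is a clause in each section and one clarifying sentence, with no new visits or samples. The downside is a possible earlier pause for DSMB review in a ten-subject study, including for a child being supported with transfusions who would have recovered late.
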